7. STATISTICAL CONSIDERATIONS

7.1. Statistical Hypotheses

The following statistical hypotheses will be tested in a hierarchical manner:

 H_{01} : pFCI - pP = 0 H_{11} : pFCI - pP < 0

 $H_{02}: pFC - pP = 0$

 $H_{12}: pFC - pP < 0$

where pFCI represents the proportion of participants with at least one COVID-19–related medically attended contact, due to increased symptom severity, or death due to COVID-19 rate through Day 30 for the famotidine/celecoxib combination, pFC represents the relative frequency of the same parameter for the famotidine/celecoxib combination, and pP the relative frequency for placebo.

7.2. Sample Size Determination

The sample size was estimated assuming that an interim analysis with stopping criteria for futility will be performed after 50% of participants have a primary endpoint assessment at Day 30. The O'Brien-Fleming beta-spending function is used to determine the non-binding futility boundary.

A total of 1318 evaluable participants, defined as part of the Full Analysis population (659 per group) are required to detect a relative reduction in the primary efficacy parameter of 60% in the active treatment arms compared to placebo (from of 6% in the placebo group to 2.4% in the active groups) with 90.0% power and using a two-sided χ^2 -test with 0.5% significance level, assuming variances are pooled, and that continuity correction was not used. Assuming a 10% screen failure rate, 1465 enrolled participants will be required.

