Statistical Methods: The study will aim to enroll up to 1465 participants, which assumes a 10% screen failure rate, with a final allocation of 659 participants in the treatment arm and 659 in the control arm.

This sample size of ensures a power of 90% at a 2-sided α of 5%, assuming a 1:1 randomization, a placebo rate of 6% (of participants with at least one COVID-19–related medically attended contact, due to increased symptom severity, or incidence of death due to COVID-19 through Day 30) and an assumed relative risk reduction of 65% to 2.4% in the active treatment arms. The statistical test of the null hypothesis of no between-group difference in proportions, as specified

in the primary endpoint, will be tested using a χ^2 test at a two-sided 5% significance level. An interim analysis for futility will be performed after 50% of participants have completed the primary endpoint assessment at day 30. Safety analyses will be performed on the Safety Population, consisting of all participants who are randomized and received study drug, analyzed by actual treatment arm. A more detailed description of the statistical methods can be found in Section 7.

Protocol Title: A virtual Phase 2 randomized, placebo-controlled, double-blind study to evaluate the safety and efficacy of the combination of famotidine and celecoxib as a post-exposure prophylaxis (PEP) for newly-infected COVID-19 patients.

Short Title: LEAP-CT as a post-exposure prophylaxis for newly-infected COVID-19 patients.

Rationale: Please refer to the Master Protocol LDOS-21-001 for a comprehensive background and rationale for this study of a combination of famotidine and celecoxib as post-exposure prophylaxis (PEP) for newly-infected COVID-19 patients.

Overall Design: This is a Phase 2, randomized double-blind placebo-controlled decentralized virtual study in which outpatient participants, newly diagnosed for COVID-19, will be randomized in a 1:1 ratio to one of two study groups (1 treatment group and 1 control group). The study is designed as a virtual trial in that it will be conducted, *in situ*, with home-based participants entering self-assessments via a web-enabled adaptive platform – The participants will be under the oversight of regionally based investigators who will be responsible for study conduct and the review of blinded data on a periodic basis.

Intervention Groups and Duration: The treatment regimen for this study is shown in Table 4.

Regimen	Dose	# of Participants

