7.4.2. Efficacy Analyses

The **primary efficacy** endpoint, the percentage of patients with at least one COVID-19–related medically attended contact, due to increased symptom severity or death (all-cause mortality) through Day 30, will be analyzed using a two group χ^2 test with pooled variances and no continuity correction. Statistics and the associated 95% confidence interval will be provided. The primary efficacy analysis will be performed using the ITT and will be repeated for robustness purposes with the PP.

In case of missing data of the primary endpoint at day 30 (Visit 4), the primary analysis will consider participants (with missing primary endpoint data until day 30) as having at least one medically attended visit. For sensitivity purposes, the primary efficacy analysis will be repeated by excluding participants with missing primary endpoint until day 30 (Complete Case Analysis).

The **secondary safety endpoints**: Incidence of Related Serious Adverse Events (SAE), Incidence of discontinuation due to related SAE and Incidence of death will also be analyzed using a χ^2 test. Descriptive statistics including exploratory confidence intervals/p-values will be provided.

All **other efficacy endpoints** will be analyzed in an exploratory manner by applying appropriate statistical methods (e.g. χ^2 test for incidences, log rank test and Kaplan Meier method for cumulative incidences, ANOVA for continuous variables) using the FAS set. Descriptive statistics including exploratory confidence intervals/p-values will be delivered.

All **other safety related endpoints** will be analyzed in a descriptive way by providing descriptive statistics and/or shift tables from baseline to the assessment visits.

For more details of the statistical analysis, methods/models refer to the SAP.

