7.4.3. Interim Analyses

An interim analysis with stopping criteria for futility and validation of sample size is planned after 50% of the participants have completed the primary endpoint assessment at Day 30 (Visit 4).

To prevent power loss due to this interim analysis, a beta-spending function was used to calculate stopping bound according to O'Brien and Fleming (Lan, 1983) (O'Brien, 1979). The futility bound for difference in proportions between active treatments and placebo is 0.0232 in the interim analysis. The nominal level of significance is not affected α =0.05 (two-sided) and 90% power is kept for the final analysis. The interim analysis will be performed on the Full Analysis set.

If the primary endpoint is missing at Day 30, the participant will be excluded from the interim analysis (Complete Case Analysis). The interim efficacy analysis will be performed using a two-group chi-square test comparing the FCI combination with placebo followed by the FC–placebo comparison.

If the study is not stopped due to futility after the interim look, the assumptions for the sample size determination will be checked and the sample size may be increased if a decrease in treatment difference by more than 10% (due to a lower placebo rate and/or due to a higher rate in the active arms) is observed.

The SAP will describe the planned interim analyses in greater detail.

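### Section 7.2 gives the sample size at a two-sided 0.5% level and the synopsis gives a 65% reduction; 659 per group fits only 5% and 60%

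*Protocol*

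**What the plan says.** **Significance level**

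- Section 7.2 (Sample Size Determination) bases 1318 evaluable participants, 659 per group, on 90.0% power and a two-sided χ² test "with 0.5% significance level, assuming variances are pooled, and that continuity correction was not used".
- The synopsis (Section 1.1, Statistical Methods) describes the same sample size as giving "power of 90% at a 2-sided α of 5%, assuming a 1:1 randomization". It then says the primary null hypothesis will be examined by a χ² "test at a two-sided 5% significance level".
- Section 7.4.3 (Interim Analyses) says: "The nominal level of significance is not affected α =0.05 (two-sided) and 90% power is kept for the final analysis".
- Section 7.4.2 (Efficacy Analyses) attaches a 95% confidence interval to the primary result: "Statistics and the associated 95% confidence interval will be provided".

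**Effect size**

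- The synopsis gives a placebo rate of 6% and "an assumed relative risk reduction of 65% to 2.4% in the active treatment arms".
- Section 7.2 gives the same two rates and calls them "a relative reduction in the primary efficacy parameter of 60% in the active treatment arms compared to placebo".

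**The concern.** Two printed figures conflict with the rest of the document.

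The first is the level. Section 7.2 is the formal sample-size statement, and its level is one tenth of the level used everywhere else. If 0.5% were meant, the trial would be far too small. If 5% was meant, the sentence is false as written. Should anyone treat the Section 7.2 figure as the success criterion, any p-value between 0.005 and 0.05 would be open to dispute after unblinding.

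The second is the effect. The synopsis pairs a percentage reduction with rates that do not produce it. This matters beyond tidiness because Section 7.4.3 has the design assumptions re-examined at the interim and allows a larger sample if the treatment difference has shrunk by more than 10%. The planned difference is 3.6 percentage points under 60% (6 − 2.4) and 3.9 under 65% (6 − 2.1). The trigger would then be a difference below 3.24 points (0.9 × 3.6) or below 3.51 points (0.9 × 3.9).

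**Working it through.** **Inputs.** Placebo rate p₁ = 0.06 and active rate p₂ = 0.024 (synopsis and Section 7.2). Power 90%, 1:1 allocation, 659 per group. Pooled variance without continuity correction (Section 7.2). Two-sided α of 0.05 (synopsis, Section 7.4.3) or 0.005 (Section 7.2).

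**Step 1: relative reduction.** 1 − 0.024/0.06 = 0.60. A 65% reduction would give 0.06 × (1 − 0.65) = 0.021, that is 2.1%.

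**Step 2: sample size per group.**

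n = [z₁₋α/₂ · √(2p̄(1−p̄)) + z₀.₉₀ · √(p₁(1−p₁) + p₂(1−p₂))]² / (p₁ − p₂)²

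For 6% versus 2.4%: p̄ = 0.042, the first root is 0.2837, the second is 0.2825, and the difference is 0.036.

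- α = 0.05: n = [(1.960 × 0.2837 + 1.2816 × 0.2825) / 0.036]² = 650.4, so 651. This reproduces the protocol's 659 to within about 1.3%.
- α = 0.005: n = [(2.807 × 0.2837 + 1.2816 × 0.2825) / 0.036]² = 1035.3, so 1036. That is 57% more than 659.

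**Step 3: power at 659 per group.**

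Power = Φ{ [(p₁ − p₂)√659 − z₁₋α/₂ · √(2p̄(1−p̄))] / √(p₁(1−p₁) + p₂(1−p₂)) }

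- α = 0.05: Φ[(0.9242 − 0.5560)/0.2825] = Φ(1.303) = 90.4%.
- α = 0.005: Φ[(0.9242 − 0.7963)/0.2825] = Φ(0.453) = 67.5%.

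An exact binomial check gives 91.5% and 68.9%.

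**Step 4: all four combinations.**

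| Two-sided α | Reduction (active rate) | n per group for 90% | Power at 659 |
|---|---|---|---|
| 5% | 60% (2.4%) | 651 | 90.4% |
| 5% | 65% (2.1%) | 535 | 94.9% |
| 0.5% | 60% (2.4%) | 1036 | 67.5% |
| 0.5% | 65% (2.1%) | 852 | 78.5% |

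Other conventions do not rescue 0.5%. With 2.4% active, one-sided, unpooled or continuity-corrected versions need 922 to 1091 per group.

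**Step 5: the futility look.** Section 7.2 says the sample size allows for a non-binding futility look at 50%, with O'Brien-Fleming beta spending. Assuming the Lan-DeMets O'Brien-Fleming-type function, the β spent at the look is 0.020 and the inflation factor is 1.0217. Then 650.4 × 1.0217 ≈ 664 per group, and 659 gives 89.8% power at 5%. The stated 659 lies between the fixed-design 651 and this 664.

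**Step 6: enrolment.** 1318 / (1 − 0.10) = 1464.4, so 1465, as stated.

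**Step 7: the zone between the two levels.** Under the design rates, the chance of a p-value between 0.005 and 0.05 is 90.4% − 67.5% = 22.9%. As an example, take 40 of 659 placebo participants with an event. Then 24 active events give p = 0.040 and 25 give p = 0.056; 18 give p = 0.003 and 19 give p = 0.0052. So 19 to 24 active events would pass at 5% and fail at 0.5%.

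**The case against.** The strongest reply is that 0.5% is an evident slip with no operational effect. It appears only in the account of how the sample size was derived. The one sentence that sets the level of the primary test is in the synopsis and says 5%, and Section 7.4.3 confirms 5% for the final analysis. A reader following the stated test rule would use 5%, so the 23% zone arises only if someone applied the Section 7.2 figure to the test. That is fair, and the 23% should be read as conditional on such a misreading.

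The 65% is weaker still as a concern. Both sections print the same rates, those rates drive the sample size, and a true 65% reduction would raise power to 94.9%. This half is editorial, apart from its bearing on the interim check.

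The 95% confidence interval in Section 7.4.2 is a common reporting convention and adds little. The case does not need it.

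Finally, with the futility look 659 gives 89.8% power, not exactly 90%. The gap is 0.2 percentage points and depends on an assumed spending function, so the stated 90% holds to rounding.

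None of this makes the Section 7.2 sentence true. Nor can the matter be left to the SAP, because the protocol states conflicting values; it has not merely omitted a detail.

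**Conclusion.** The point holds. Section 7.2's level and the synopsis's percentage reduction are both wrong as written. Of the four combinations the protocol's figures allow, only a two-sided 5% level with a 60% reduction makes 659 per group the sample size for about 90% power. At the printed 0.5%, power would be 67.5% and 1036 per group would be needed.

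The correction should be made, chiefly because the formal sample-size section should carry the right significance level; the 65% is secondary. The trial is not underpowered at 5%. The main figures rest on the fixed-design pooled formula that Section 7.2 names. The 664 per group and 89.8% power also assume Lan-DeMets O'Brien-Fleming-type beta spending at half the information.

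**What to change.** - **Section 7.2:** replace 0.5% with 5% as the two-sided significance level.
- **Synopsis, Statistical Methods:** replace 65% with 60% as the relative risk reduction, keeping the rates of 6% and 2.4%.

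The sponsor should confirm both against the original sample-size output before amending. The 659 per group, 1318 evaluable and 1465 enrolled then stand, with 90% power to within rounding. The cost is two one-number text corrections by amendment, best made before any unblinded look. Nothing changes in the test, the sample size or enrolment.

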7.3. Populations for Analyses

For purposes of analysis, populations are defined in Table 8.

Population	Description
Enrolled	All participants that have signed the Informed Consent Form, met the eligibility criteria, were randomized to study intervention, discontinued before first intake (Screening failures) or received at least one of study medication (Intent-To-Treat (ITT), Safety)
Full Analysis (FAS)	All participants who were randomized and received at least one dose of study medication. Participants in the FAS/ITT will be analyzed as randomized.

Table 8:Analysis Populations

Population	Description
Per Protocol (PP)	All participants who were included in the ITT, completed at least the 30-day assessments, and had no major protocol deviations that could have an influence on the primary efficacy endpoint. Participants in the PPS will be analyzed as treated.
Safety	All participants randomly assigned to study intervention and who take at least one dose of study intervention. Participants will be analyzed according to the intervention they actually received.

Participants excluded from the analysis sets mentioned above will be determined during the Blinded Data Review (BDR) and reasons for exclusions will be documented in the BDR report.

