1.4.2. Endpoints

Primary efficacy endpoint will include the percentage of participants with at least one COVID-19–related medically attended contact, due to increased symptom severity, through Day 30 in both the placebo and the investigational treatment population, or incidence of death (all-cause mortality). Medically-attended visits could include telemedicine visits, in-person physician visits, urgent care or emergency department visits, hospitalization.

Secondary endpoints will include the incidence of related serious adverse events (SAEs) and the incidence of discontinuation due to related SAEs, as well as oxygenation status (oxygen saturation \leq 94%, necessitating supplemental oxygen as measured by daily pulse oximeter ratings).

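### The per-protocol set requires completed 30-day assessments with no exception for death, so early deaths, which are primary events, drop out of the robustness analysis

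*Protocol*

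**What the plan says.** Table 8 in Section 7.3 sets three conditions for the PP set: membership of the ITT, that participants "completed at least the 30-day assessments", and no major deviation that could influence the primary endpoint. The second condition stands on its own and has no exception for death. The full analysis set, which Table 8 treats as the ITT, has no completion condition: "All participants who were randomized and received at least one dose of study medication".

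Death is a primary event. Section 7.4.2 describes the endpoint as a COVID-19-related medically attended contact "due to increased symptom severity or death (all-cause mortality) through Day 30", and Section 1.4.2 likewise has "or incidence of death (all-cause mortality" (all causes). Section 7.1 is narrower, with "or death due to COVID-19 rate through Day 30", and the Statistical Methods paragraph of the synopsis also counts only COVID-19 deaths.

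Section 7.4.2 gives the PP set its role: "The primary efficacy analysis will be performed using the ITT and will be repeated for robustness purposes with the PP". For the primary analysis, a participant whose endpoint is missing through Day 30 is counted "as having at least one medically attended visit". A complete-case sensitivity analysis leaves such participants out.

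**The concern.** Someone who dies on Day 12 cannot complete the 30-day assessments. That person has a fully known primary outcome, yet Table 8 removes them because of that outcome. A per-protocol set is meant to drop participants for departures from the protocol. A condition that an endpoint event makes impossible to meet selects on the outcome after randomisation.

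The PP repeat is there to show whether the ITT result is robust. If early deaths fall mainly on placebo, the PP difference shrinks and may seem to weaken a sound ITT result. If they fall mainly on active, it grows and conceals the most serious outcome in the trial. The two analyses also pull in opposite directions: the ITT counts unknown outcomes as events, while the PP set deletes known ones.

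**Working it through.** **Step 1: the definitions side by side.**

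| Participant | Primary outcome known? | In ITT? | In PP set as written? |
|---|---|---|---|
| Dosed, dies before Day 30 | Yes, event | Yes | No, cannot complete Day 30 |
| Dosed, completes Day 30, no relevant major deviation | Yes | Yes | Yes |
| Dosed, no event recorded, lost before Day 30 | No | Yes, counted as event | No |

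The first row is the fault. It holds for all deaths under the all-cause wording (Sections 1.4.2 and 7.4.2) and for COVID-19 deaths under the narrower wording (Section 7.1).

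**Step 2: the plan's own figure.** Section 7.2 gives 6% on placebo, 2.4% on active, 90% power, pooled χ² test, no continuity correction, 659 per group. The level used here is the two-sided 5% of the synopsis and Section 7.4.3. Section 7.2 prints 0.5%, but that would need 1036 per group.

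n = [1.960·√(2·0.042·0.958) + 1.282·√(0.06·0.94 + 0.024·0.976)]² / 0.036² = 651 per group.

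The stated 659 is close, and the small excess is compatible with the futility look. Power at 659 is 90.4%. Expected events are 659 × 0.06 = 39.5 on placebo and 659 × 0.024 = 15.8 on active.

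**Step 3: the effect of deleting deaths.** Let d be the proportion of an arm that dies before Day 30, included in the event rate p. The PP rule takes these participants out of numerator and denominator:

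p′ = (p − d) / (1 − d)

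The protocol gives no death rate, so every d below is an assumption.

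| d placebo / active | Deaths per 659 | PP rates | Difference (points) | Risk ratio |
|---|---|---|---|---|
| 0 / 0 | 0 / 0 | 6.00% / 2.40% | 3.60 | 0.400 |
| 0.1% / 0.04% | 0.7 / 0.3 | 5.91% / 2.36% | 3.54 | 0.400 |
| 0.5% / 0.2% | 3.3 / 1.3 | 5.53% / 2.20% | 3.32 | 0.399 |
| 1% / 0.4% | 6.6 / 2.6 | 5.05% / 2.01% | 3.04 | 0.398 |
| 0.5% / 0 | 3.3 / 0 | 5.53% / 2.40% | 3.13 | 0.434 |
| 0 / 0.5% | 0 / 3.3 | 6.00% / 1.91% | 4.09 | 0.318 |

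For example, at 1% / 0.4%: (0.06 − 0.01)/0.99 = 0.0505 and (0.024 − 0.004)/0.996 = 0.0201.

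When deaths follow the planned 60% reduction, the absolute difference shrinks but the risk ratio barely moves. When deaths are uneven, both move, in either direction.

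**Step 4: check on a wider remedy.** One could also keep anyone with an earlier medically attended contact who then misses Day 30. Event-free non-completers would still be excluded. If 10% of event-free participants do not complete (assumption) and all events are kept:

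- placebo: 0.06 / (0.06 + 0.94 × 0.9) = 0.06 / 0.906 = 6.62%
- active: 0.024 / (0.024 + 0.976 × 0.9) = 0.024 / 0.9024 = 2.66%

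The difference becomes 3.96 points instead of 3.60, so the wider rule distorts upward.

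**The case against.** The strongest reply is that little depends on this set. The primary analysis is on the ITT, no decision rule uses the PP result, and deaths should be few in ambulatory participants when the endpoint counts any related telemedicine or physician contact. All of that stands, and it limits the importance of the point.

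A second reply is that Section 7.4 leaves the description of populations to the SAP, and Section 7.3 has exclusions settled at a blinded data review. An exception could be written there. But the protocol has already fixed the condition without one, and blinding to treatment does not stop selection on outcome.

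Three stronger readings are tempting, and the protocol does not support them:

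- **Hospitalised participants are lost too.** Section 3.8.1 says participants hospitalised for worsening COVID-19 continue to be followed for outcome, and note 3 to Table 5 makes all visits remote. Some may still miss Day 30, but only death necessarily prevents completion.
- **A sizeable share of events, say 5% to 20%, would be deleted.** Nothing in the protocol anchors such a share. If 20% of placebo events were deaths, placebo mortality would be 0.20 × 6% = 1.2%.
- **The complete-case and interim analyses share the fault.** Sections 7.4.2 and 7.4.3 exclude participants whose primary endpoint is missing, not those who missed a visit. A participant who has died has a known endpoint and stays in.

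**Conclusion.** The point holds for deaths in the PP set. Followed as written, Table 8 removes every participant who dies before Day 30 from the stated robustness analysis, although the death is a primary event. This is a rule stated wrongly, not a detail left for later.

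The effect is probably small: 0.06 to 0.56 points off a planned difference of 3.60 over the proportional mortality range assumed above. The direction is not guaranteed. Deaths of 0.5% on active only would raise the PP difference to 4.09 points and hide harm. These sizes rest on assumed death rates, the planned event rates, and otherwise complete follow-up. The ITT result and the sample size do not change.

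**What to change.** In Table 8, change the completion condition to *completed the 30-day assessments or died before Day 30*, leave the major-deviation condition as it is, and state that these deaths count as events. Use one definition of the death component throughout, since Sections 1.4.2 and 7.4.2 count all causes and Section 7.1 only COVID-19.

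If the sponsor also wants to keep participants with an earlier medically attended contact who then miss Day 30, the text should admit the cost: event-free non-completers stay excluded, which raises the event rates (Step 4).

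The complete-case and interim rules can stay as they are. The change costs one clause in Table 8, matched in the SAP, with no new data and no change to the sample size.
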